4.2 Pre-Intervention

All patients will have an esophageal balloon catheter inserted into their nare while upright (head of bed > 30 degrees) to a depth slightly more than the estimated distance from the lower sternum to the back of the ear (typically around 60 cm). Gastric positioning will be confirmed with abdominal compression testing and the catheter then retracted 10 – 20 cm into the lower esophagus. Placement will be confirmed with the presence of cardiac oscillations on the esophageal probe. The probe will then be secured to the patient's nasal opening using tape.

Pressures [Esophageal Pressure (P_{es}), Airway Pressure (P_{aw}), and Transpulmonary Pressure (P_{tp})] are measured directly through the ventilator. The waveforms of P_{aw} , P_{es} , and P_{tp} will be visualized on the ventilator. P_{tp} is obtained from $P_{aw} - P_{es}$. All patients will have baseline measurements recorded of ICP, CPP, HR, and MAP.

4.3 Intervention

PEEP will be increased on the ventilator to achieve a P_{tp} between 0 and +2 cm H₂O (“Optimal PEEP”).

4.4 Post-Intervention

Measurements of ICP, CPP, and MAP will be repeated 5 minutes after the change in PEEP.

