Study Phases Screening Study Treatment Follow-Up	
(1) Screening: Screening for eligibility and obtaining consent
 
(2) Pre-Intervention: Baseline data collected, including ICP monitoring every 5 minutes for 15 minutes prior to the intervention to insure patients are at a steady state as it pertains to cerebral pressures. Patients with minimal ICP variation will then have an esophageal balloon placed to measure transpulmonary pressure.
 
(3) Intervention: PEEP titrated to "optimal PEEP" based on P_{tp}
 
(4) Post-Intervention: Data collection five minutes after intervention.
 
(5) Subject Completion/Withdrawal: Ventilator management will be returned to the primary critical care team to determine PEEP going forward. In patients who continue on the titrated level of PEEP, safety data will be collected for an additional 24 hours.

Efficacy/Safety Evaluations	This study is will use endpoints of ICP, CPP, and MAP to assess the safety of PEEP titration by P_{tp} measurements via

esophageal balloon. Determination of safety will be made based on the lack of a clinically significant increase in ICP, decrease in CPP, or decrease in MAP. All patients will have continuous hemodynamic and oxygenation monitoring, in addition to ICP/ CPP monitoring, per NSICU protocol to monitor patient safety. In patients who continue on the titrated level of PEEP after the intervention (decision made by the primary critical care team), ICP, CPP, hemodynamic, and oxygenation data will be recorded for 24 hours after the intervention to evaluate for any possible adverse events, and this data will also be reported.

Statistical and Analytic Plan

The trial is an interrupted time-series design non-inferiority trial evaluating “optimal PEEP” as determined by an esophageal balloon compared to baseline standard PEEP management. The primary outcome will be intracranial pressure with a non-inferiority limit of 4 mm Hg, analyzed with a non-inferiority design. CPP and MAP are secondary outcomes with non-inferiority margin of 10 mm Hg each.

DATA AND SAFETY MONITORING PLAN

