6 STATISTICAL CONSIDERATION

6.1 Primary Endpoint

The primary endpoint is change in ICP 5 minutes after PEEP titration. the parameter representing mean increase during/after titration is > 4 (mm Hg) in the target population.

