7.2 Safety Monitoring

Data will be collected 5 minutes after the intervention, giving time for pressure equilibration from the ventilator and its effect on ICP, CPP, and MAP. Significant changes in these metrics, as defined above, will be reported as adverse events. At the conclusion of the intervention, PEEP management will be returned to the primary team. In patients whom they continue the “optimal PEEP” level, we will continue to evaluate for possible adverse events for an additional 24 hours, and this data will be reported. In addition to clinically significant changes in ICP, CPP, and MAP as defined above, additional adverse events that will be reported will include evidence of new barotrauma, change in pressor requirement, or change in HR to > 120 or < 50 .

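### ICP, CPP and MAP are judged on one reading 5 minutes after the PEEP change, and the adverse-event rule states no window, so an ICP rise or CPP fall during titration can go unrecorded

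*Combined protocol and SAP*

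**What the plan says.** Section 6.1 defines the endpoint at one time: "The primary endpoint is change in ICP 5 minutes after PEEP titration". Section 4.4 matches it: ICP, CPP and MAP "will be repeated 5 minutes after the change in PEEP". The schedule in section 5 has a pre-intervention column, one post-intervention column, and hourly columns for 24 hours that apply only to patients whom the primary team keeps on the titrated PEEP. No column covers the titration period.

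Section 6.1 then continues with an incomplete sentence that refers to "mean increase during/after titration".

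Section 7.2 gives the reason for the timing: "Data will be collected 5 minutes after the intervention, giving time for pressure equilibration from the ventilator and its effect on ICP, CPP, and MAP". The next sentence is the adverse-event rule: "Significant changes in these metrics, as defined above, will be reported as adverse events". It also lists new barotrauma, a change in pressor requirement, and a heart rate above 120 or below 50. Section 7.1 adds hypotension thought to be related to ventilation changes. Under 7.3, any patient meeting one of these parameters goes to a critical care physician independent of the study.

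The synopsis (Efficacy/Safety Evaluations) states: "All patients will have continuous hemodynamic and oxygenation monitoring", and adds ICP and CPP monitoring under the unit's own protocol. No section turns that monitoring into study data for the titration period.

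**The concern.** The objective is safety, and section 1.3 names the worry that kept such patients out of earlier trials: higher ICP and lower CPP. A reading at minute 5 describes the settled state. It cannot show what happened between the first change in PEEP and that reading. The documents do not say how long titration takes, so the unrecorded interval is at least 5 minutes and otherwise undefined.

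Treatment makes this worse. If staff respond to an ICP rise during titration and the response works, the 5-minute value looks favourable. ICP-directed treatment is neither a listed adverse event nor a field in section 5, so the dataset need hold no trace of it. The protocol recognises this kind of confounding in one form, since it excludes patients with a planned change in the drain set point during the study periods. Unplanned measures are not addressed.

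At stake is whether a conclusion of safety covers the titration manoeuvre or only the state 5 minutes later.

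**Working it through.** This is mainly a comparison of passages. Arithmetic only shows why the choice of reading could matter.

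**1. Which transients have a route into the record?** Take an event that occurs during titration and is over, or controlled, by minute 5.

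| Event | In the endpoints? | Reportable as an adverse event? |
|---|---|---|
| ICP rise, resolved or treated | No | Unclear: 7.2 gives no window, and ICP-directed treatment is not listed |
| CPP fall without hypotension or pressor change | No | Unclear on window; also see step 2 |
| MAP fall treated with pressors | No | Yes: change in pressor requirement (7.2) |
| MAP fall judged to be ventilation-related hypotension | No | Yes (7.1), though without a threshold or time window |
| Heart rate beyond 120 or 50 | Not an endpoint | Yes (7.2) |

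**2. Direction of the CPP threshold.** Section 7.2 relies on changes as defined earlier. Section 2.2a defines the significant CPP change as an increase above 10 mm Hg. Section 6.3 tests a lower bound against -10 mm Hg, and the synopsis speaks of a decrease. Read literally, the event rule does not capture a CPP fall even at minute 5.

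**3. The plan's sample sizes.** With one-sided 0.05 and 80% power, 2 × [SD × (1.645 + 0.842) / margin]² gives:

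- ICP: 2 × (4.4 × 2.487 / 4)² = 15.0, stated 15.
- CPP: 2 × (11.3 × 2.487 / 10)² = 15.8, stated 16.
- MAP: 2 × (11.8 × 2.487 / 10)² = 17.2, stated 18.

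The figures reproduce, but with a formula for two independent groups. The paired formula without the factor 2 gives 8, 8 and 9. It is therefore not certain that 4.4 is the SD of the within-patient change, and step 4 gives a range.

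**4. Sensitivity of the conclusion (illustration).** Non-inferiority is concluded when mean change + t × SD/√n is below 4. The largest mean that passes is:

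- n = 18, SD 4.4: 4 - 1.740 × 4.4/√18 = 2.20 mm Hg.
- n = 25 (all enrolled, as 6.3 could imply), SD 4.4: 4 - 1.711 × 4.4/√25 = about 2.5 mm Hg.
- n = 18, SD 4.4 × √2 = 6.2: 4 - 1.740 × 6.2/√18 = about 1.45 mm Hg.

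With n = 18 and SD 4.4, the chance of passing is 0.98, 0.87, 0.58, 0.24 and 0.05 at true mean changes of 0, 1, 2, 3 and 4 mm Hg. With SD 6.2 it is 0.83, 0.63, 0.37, 0.16 and 0.05. A gap of 1 or 2 mm Hg between peak and 5-minute change could therefore alter what is concluded about the peak. Nothing in the documents says whether such a gap exists.

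**The case against.** Five minutes is a reasoned choice. Section 7.2 justifies it by equilibration, the primary objective concerns the effect of titrating to the target, and no section names transient change as the quantity of interest. Patients kept on the titrated PEEP also have hourly data for 24 hours. This stands, and it is why the 5-minute value should remain primary.

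A reader might infer that any transient is excluded from the adverse-event count. The documents do not support that. Pressor changes, ventilation-related hypotension and heart-rate limits are reportable whenever they occur. Section 7.2 does not confine its ICP, CPP and MAP thresholds to the 5-minute value, so staff watching a continuous monitor could report a spike. For ICP and CPP the rule is ambiguous; it is not an exclusion. The ambiguity still means that reporting depends on how each reader takes the sentence.

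A reader might also infer that the result is biased toward safety by a calculable amount. It is easy to construct a case: a patient who peaks at +10 mm Hg and reads +1 at minute 5 removes (10 - 1)/18 = 0.5 mm Hg from the mean peak rise. That profile is invented, and its frequency is unknown.

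Finally, the phrase in 6.1 is a fragment, and its alternative wording can be met by a reading taken afterwards. It shows unclear drafting rather than a firm contradiction. It still needs tidying, because no measurement corresponds to its first half.

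**Conclusion.** The point holds in a limited form. The ICP, CPP and MAP endpoints rest on one reading 5 minutes after the PEEP change, and section 7.2 gives no window for its thresholds. A rise in ICP or fall in CPP that has resolved or been treated by then is missing from the endpoints and may go uncounted as an adverse event. For MAP the gap lies in the endpoint; a pressor-treated fall, or one judged to be ventilation-related hypotension, already has a reporting route.

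No size of bias can be given, because the documents contain nothing on how often or how far values move during titration. The passing limits of about 1.45 to 2.5 mm Hg rest on the stated assumptions about n and SD, and show only that the choice of reading could matter. The primary analysis need not change. The change is a worthwhile, cheap improvement to the safety record.

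**What to change.** 1. Keep the 5-minute change as the primary endpoint.
2. From the monitoring already running, record the highest ICP and the lowest CPP and MAP from the first change in PEEP to the 5-minute reading.
3. Record the same extremes over an equally long, settled window before titration that starts after balloon placement. Section 7.1 notes that placement can provoke cough or vomiting, and a window that includes it could raise the baseline extreme and mask a titration peak.
4. Record any ICP- or pressure-directed treatment given from the start of titration to minute 5.
5. Report the changes in extremes descriptively, as supportive secondary safety data.
6. State in 7.2 that the adverse-event window runs from the start of titration, and send threshold crossings to the independent review already set up in 7.3.
7. Complete the sentence in 6.1 and align it with the windows chosen.
8. Reconcile the direction of the CPP threshold in 2.2a with 6.3.

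The cost is six fields for extremes (three measures in two windows) and one for treatment; the sample size is unaffected. The documents do not say whether monitor data are stored and retrievable; if they are not, the values must be noted at the bedside. Extremes are noisier than a single reading. A matched window removes the average effect of taking extremes but not the variation within a patient, so some flagged events will be noise. That is why the extremes stay supportive and crossings go to review.

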4.5 Subject Completion/ Withdrawal

At the conclusion of the intervention, the trial will be completed. Ventilator management will be returned to the primary critical care team who will determine PEEP level going forward. In patients who are maintained thereafter on the “optimal PEEP”, safety data will be collected for an additional 24 hours.

5 STUDY EVALUATIONS AND MEASUREMENTS

	Pre-Intervention	Post-Intervention	Hourly x 24 Hours*
ICP	X	X	X
CPP	X	X	X
MAP	X	X	X
HR	X	X	X
SpO ₂	X	X	X
FiO ₂	X	X	X
PEEP	X	X	X
P _{tp}	X	X	
P _{aw}	X	X	
P _{es}	X	X	
Age	X		
BMI	X		
Diagnosis	X		

*Hourly data collected in patients who are continued on "optimal PEEP at the discretion of the primary team.

6 STATISTICAL CONSIDERATION

6.1 Primary Endpoint

The primary endpoint is change in ICP 5 minutes after PEEP titration. the parameter representing mean increase during/after titration is > 4 (mm Hg) in the target population.

6.2 Secondary Endpoints

1. CPP before and after intervention.
2. MAP before and after intervention.
3. Adverse events will be evaluated by the frequency, type, and severity, and these data will be reported

6.3 Statistical Methods

All endpoints will be described in term of means and standard deviation, with associated 95% confidence intervals, and median [Q1-Q3]

The change in ICP will be analyzed with a non-inferiority study: the ICP value after intervention will be considered equivalent to the ICP before intervention if the 95% upper bound of the change is lower than the non-inferiority margin of 4 mm Hg.

In a similar manner, the CPP and MAP values before and after intervention will be considered equivalent if the 95% lower bounds of the respective changes are higher than -10 mm Hg.

Should the 95% upper bounds of ICP be higher than 4, the effect of the intervention would be considered inconclusive. Similarly if the equivalence of CPP and MAP cannot be observed, the intervention will be reported inconclusive for these endpoints.

Adverse events will be reported.

By study design, all patients will be monitored in the ICU for the duration of the study and missing values are not expected. However, in the unlikely event that missing values would be present, the subjects will not be excluded and statistics will be calculated on all available data. The dataset for analysis will consist of all subjects regardless of protocol deviation, as an Intent-to-treat population.

Additional data points from the table above will be collected and tabulated using mean and standard deviation.

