2.1 Primary Objective

To determine that titration of PEEP to optimal PEEP does not result in clinically significant changes in ICP (defined as an increase in ICP > 4 mm Hg).

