6.4 Sample Size and Power

Based on a non-inferiority trial design using a one-sided 95% confidence interval, a power of 80%, a non-inferiority limit of 4 mm Hg for ICP, and a standard deviation of 4.4 mm Hg based on previously published data (11), the study will need 15 participants who require a change in PEEP based on esophageal balloon measurements. To evaluate our secondary goals, using a non-inferiority limit of 10 mm Hg for CPP and a standard deviation of 11.3, we would need 16 subjects, and using a non-inferiority limit of 10 mm Hg for MAP and a standard deviation of 11.8, we would need 18 subjects.

Since we estimate that 29% will not need a change in PEEP (2), we expect we will need to enroll 25 participants and obtain esophageal balloon pressure measurements in order to have 18 participants requiring changes in PEEP.

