7.3 Adverse Event Reporting

“Possible Adverse Event” will be defined as a patient meeting any of the above parameters. Each possible adverse event will be reviewed by a UNC critical care physician who is independent of the study within 72 hours. After independent review, events considered to be likely or definitely related to the intervention will be submitted to the IRB for review.

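### The 6.3 verdict of equivalent ICP rests on the mean change alone, so it cannot by itself show the absence of clinically significant rises, which the plan defines by the same 4 mm Hg

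*Combined protocol and SAP*

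**What the plan says.** The 4 mm Hg figure has two roles in the combined protocol and SAP.

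- **Patient level.** The primary objective (2.1) is that titration "does not result in clinically significant changes in ICP (defined as an increase in ICP > 4 mm Hg"). Section 7.2 adds: "Significant changes in these metrics, as defined above, will be reported as adverse events". Section 7.3 says that a possible adverse event "will be defined as a patient meeting any of the above parameters". Together these make a rise above 4 mm Hg an event in an individual patient.
- **Mean level.** Section 6.1 refers to "the parameter representing mean increase during/after titration is > 4 (mm Hg) in the target population". Section 6.3 states that "the ICP value after intervention will be considered equivalent to the ICP before intervention if the 95% upper bound of the change" is below the 4 mm Hg margin, and treats CPP and MAP the same way with lower bounds above -10 mm Hg.

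The synopsis (Efficacy/Safety Evaluations) says: "Determination of safety will be made based on the lack of a clinically significant increase in ICP". It says the same for decreases in CPP and MAP.

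Adverse events are a secondary endpoint in 6.2, to be summarised by how often they occur, their kind and their severity. Section 6.3 says only that they will be reported. It gives them no role in the ICP conclusion and attaches no interval to them.

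**The concern.** A bound on a mean limits the average change. Patients whose ICP falls or stays flat offset those whose ICP rises, so the bound can lie below 4 mm Hg while a fair number of individuals exceed 4 mm Hg. Because one number serves both purposes, a reader can easily take the verdict on the mean as an answer to the patient-level question in the synopsis. The word *equivalent* adds to this: the rule is one-sided and supports only non-inferiority of the mean. At stake is what the trial may claim against its own safety objective. The validity of the mean analysis is not in question.

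**Working it through.** **Inputs.** Margin and patient threshold 4 mm Hg (2.1, 6.3); SD 4.4 mm Hg (6.4); 18 patients needing titration (3.2, 6.4). Section 6.4 begins "Based on a non-inferiority trial design using a one-sided 95% confidence interval, a power of 80"%. Section 6.3 does not say whether its upper bound is one-sided or the upper limit of a two-sided 95% interval, so both are shown.

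**The plan's own sample size.** The two-independent-sample formula, per group, is n = 2 × SD² × (1.645 + 0.842)² / margin².

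- ICP: 2 × 4.4² × 6.18 / 4² = 15.0, so 15.
- CPP: 2 × 11.3² × 6.18 / 10² = 15.8, so 16.
- MAP: 2 × 11.8² × 6.18 / 10² = 17.2, so 18.

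All three match 6.4. A paired calculation with 4.4 as the SD of change would give 8 (normal) or 9 (t) for ICP. Section 6.4 does not say which SD 4.4 is. If it is the SD of single ICP values with no pre-post correlation, the SD of change is 4.4 × √2 = 6.22. Both values are carried below.

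**Largest mean change that still passes.** This is 4 - t × SD / √n, with n = 18.

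- One-sided 95%, SD 4.4: 4 - 1.740 × 4.4 / √18 = 2.20 mm Hg (1.45 with SD 6.22).
- Two-sided 95%, SD 4.4: 4 - 2.110 × 4.4 / √18 = 1.81 mm Hg (0.91 with SD 6.22).

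**Share above 4 mm Hg at that mean, with normal changes.** The distance from the passing mean to 4 is t × SD / √n. Divided by SD, it is t / √n, so the SD cancels and the share is 1 - Φ(t / √n).

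- One-sided: 1 - Φ(1.740 / 4.243) = 34.1%, about 6 of 18.
- Two-sided: 1 - Φ(2.110 / 4.243) = 30.9%.
- Over n = 15 to 25 and both readings of the bound: 29% to 37%.

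**Away from the boundary.** At a true mean change of zero the share is 1 - Φ(4 / SD): 18.2% with SD 4.4 and 26.0% with SD 6.22. With SD 3 (an assumption not found in the documents) it is 9.1%.

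Simulated trials with n = 18 and the one-sided bound (200,000 per setting) give:

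| SD of change | True mean | Trials that pass | Mean share above 4 among passing trials | At least 6 of 18 above 4 among passing trials |
|---|---|---|---|---|
| 4.4 | 0 | 98% | 18% | 8% |
| 4.4 | 1 | 87% | 23% | 19% |
| 4.4 | 2 | 58% | 26% | 31% |
| 6.22 | 0 | 84% | 24% | 21% |
| 6.22 | 1 | 62% | 26% | 30% |
| 6.22 | 2 | 37% | 28% | 37% |

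**What 18 patients can show about the proportion.** With 0 of 18 above the threshold, the one-sided 95% upper limit is 1 - 0.05^(1/18) = 15.3%. The upper limit of the two-sided exact 95% interval is 1 - 0.025^(1/18) = 18.5%. With 6 of 18 the two-sided exact interval is 13.3% to 59.0%.

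**The case against.** The strongest reply is that the plan already collects and reports what is asked for. Adverse events are a secondary objective (2.2c) and a secondary endpoint (6.2), 7.2 makes a significant ICP change one of them, and 7.3 counts by patient. Section 6.3 also promises SDs and medians with quartiles, which show spread. This stands: individual rises are not hidden. A reader might infer that the relatedness review in 7.3 would filter them out, but that review decides only which events go to the IRB. What remains is that the count has no interval and does not enter the conclusion. It may also include events from the following 24 hours in patients who stay on the titrated PEEP, so it is not necessarily a count at the 5-minute reading.

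A second reply is that 2.1 does not itself say *per patient*, and 6.1 names the mean. That is correct. The patient-level reading comes from 7.2 and 7.3, which refer back to the same definition.

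A third is that a rise above 4 mm Hg between two readings need not be caused by PEEP. Some rises may be spontaneous variation, although exclusion 9 in 3.3 removes patients whose ICP was unstable in the preceding 15 minutes. The shares above are therefore not counts of patients harmed by the intervention.

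**Conclusion.** The point holds in a limited form. The 6.3 rule can establish that the mean ICP change is non-inferior. It cannot by itself establish the lack of clinically significant rises that the synopsis sets as the basis for safety, and the plan gives no separate reason for using 4 mm Hg as a margin on the mean.

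A reader might infer that a positive trial should be expected to have a third of its patients above the threshold, or that the plan's SD produces that figure. The documents support neither. About a third (31% to 34% at n = 18) is the just-passing case. It assumes roughly normal changes and a population mean equal to the largest passing mean, and it would arise in any such test of this size whose margin equals the patient threshold. With no mean effect the share is about 18% to 26%, depending on which SD 4.4 is, and lower if changes vary less than either value implies.

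The mean analysis and its reporting of adverse events remain sound. This is an inexpensive correction to what may be concluded.

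**What to change.** In 6.3:

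1. For ICP, CPP and MAP, replace the statement of equivalence with one that the mean change is non-inferior.
2. Beside each mean result, report the number and proportion of titrated patients who cross the plan's own patient-level threshold at the 5-minute reading, with an exact 95% confidence interval. State the denominator.
3. State that the mean result alone does not support a conclusion of no clinically significant change.

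Before doing this for CPP, reconcile 2.2a, which defines the significant change as an increase, with the synopsis and 6.3, which concern a decrease. Read literally, the adverse-event definition in 7.2 inherits the 2.2a direction.

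The cost is a change of wording and three proportions from readings already scheduled in section 5. The downside is a narrower headline claim and wide intervals: even 0 of 18 leaves a one-sided 95% upper limit of 15%.

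### Section 6.3 calls ICP, CPP and MAP equivalent before and after titration on the strength of a one-sided bound, which supports only non-inferiority

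*Combined protocol and SAP*

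**What the plan says.** Section 6.3 sets the rule for the primary endpoint: ICP after titration is "considered equivalent to the ICP before intervention if the 95% upper bound of the change is lower than the non-inferiority margin of 4 mm Hg". For the two secondary pressures, "the CPP and MAP values before and after intervention will be considered equivalent if the 95% lower bounds of the respective changes are higher than" minus the margin of 10 mm Hg. The sentence on failure repeats the term: "if the equivalence of CPP and MAP cannot be observed, the intervention will be reported inconclusive for these endpoints". So equivalence is the declared conclusion for all three endpoints, and none of the three rules has a second limit.

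Elsewhere the plan names a different claim. The synopsis (study design, and statistical and analytic plan), section 1.1 and section 3.1 all describe a non-inferiority trial. Section 6.3 itself calls the ICP analysis a non-inferiority study and the 4 mm Hg a non-inferiority margin. Section 6.4 begins its calculation with "Based on a non-inferiority trial design using a one-sided 95% confidence interval, a power of 80" per cent.

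**The concern.** Equivalence means that the change lies within a margin on both sides. A single upper bound on the ICP change shows only that ICP has not risen by 4 mm Hg or more. A single lower bound on the CPP or MAP change shows only that the pressure has not fallen by 10 mm Hg or more. Read literally, 6.3 would have the report call the before and after values equivalent even if mean ICP fell, or mean CPP or MAP rose, by more than the margin. The 5% error rate does not cover that part of the statement.

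What is at stake is the published conclusion. This is an uncontrolled before-after comparison whose purpose is safety, and section 11 intends the results for journals and grant applications. Equivalent is a stronger word than non-inferior.

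The gap matters most for CPP, because the plan disagrees with itself on direction. Objective 2.2a defines a clinically significant CPP change as an increase of more than 10 mm Hg, and section 7.2 reports significant changes, as defined earlier, as adverse events. A mean CPP rise of 12.5 mm Hg could therefore be called equivalent under 6.3 while counting as significant under 2.2a.

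**Working it through.** **Inputs.** From section 6.4: "a non-inferiority limit of 4 mm Hg for ICP, and a standard deviation of 4.4 mm Hg based on previously published data"; "using a non-inferiority limit of 10 mm Hg for CPP and a standard deviation of 11.3, we would need 16 subjects"; for MAP, margin 10 mm Hg, SD 11.8 and 18 subjects; ICP needs 15. One-sided 5% error, 80% power. From section 3.2: enrolment runs until 18 patients need a PEEP increase of at least 5 cm H₂O, so n = 18 is used for all endpoints in steps 3 and 4. The true mean change is not stated; zero is assumed, and it reproduces the plan's figures.

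**Step 1: reproduce the sample sizes.** n = 2 × [SD × (1.645 + 0.842) / margin]².
- ICP: 2 × (4.4 × 2.486 / 4)² = 14.96, so 15.
- CPP: 2 × (11.3 × 2.486 / 10)² = 15.79, so 16.
- MAP: 2 × (11.8 × 2.486 / 10)² = 17.22, so 18.

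All three agree. The sizing is for a one-sided 5% non-inferiority claim. The formula implies a standard error (SE) of SD × √(2/n).

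**Step 2: check the rule as a non-inferiority rule.** Let M be the margin and s the true mean shift in the untested direction (negative s is harm as 6.3 tests it). The chance that the rule is met is Φ[(M + s)/SE − 1.645].
- At s = −M this is Φ(−1.645) = 5%, as intended.
- At s = 0 and the stated sizes it is 80.1% (ICP, 15), 80.5% (CPP, 16) and 81.5% (MAP, 18).

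So the rule, margins and sizes fit together for non-inferiority.

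**Step 3: the untested direction, s = +M, n = 18.**

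| Endpoint | True shift (mm Hg) | SE = SD × √(2/18) | 2M/SE − 1.645 | Labelled equivalent |
|---|---|---|---|---|
| ICP | −4 | 1.467 | 5.455 − 1.645 = 3.810 | 99.99% |
| CPP | +10 | 3.767 | 5.310 − 1.645 = 3.665 | 99.99% |
| MAP | +10 | 3.933 | 5.085 − 1.645 = 3.440 | 99.97% |

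A two-sided equivalence rule (two one-sided 5% tests) is met with probability Φ[(M + s)/SE − 1.645] + Φ[(M − s)/SE − 1.645] − 1. At s = M this is about 5%. At 1.25 margins (ICP −5, CPP or MAP +12.5) the written rule gives 100% and the two-sided rule about 1% or less.

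**Step 4: sensitivity.**
- If the printed SDs are SDs of the within-patient change, which the plan does not say, SE is smaller by √2 and the figures in the last column round to 100%.
- With one-sided t bounds in place of normal ones, simulation gives 99.9% to 100%.
- Section 6.3 does not say whether its bound is one-sided or the end of a two-sided 95% interval. On the second reading the lowest figure is MAP: 5.085 − 1.960 = 3.125, or 99.9%.

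**Step 5: the CPP passages side by side.** The synopsis (efficacy/safety evaluations) counts a decrease in CPP as the harm. Section 6.3 tests a lower bound of −10, which agrees with the synopsis. Section 2.2a names an increase above 10. The 6.3 rule places no limit on an increase.

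**The case against.** The strongest reply is that context settles the meaning. The ICP rule in 6.3 opens and closes with non-inferiority language, the CPP and MAP rule follows it by analogy, and no section sets a two-sided margin. On this view equivalent is a loose word for no clinically significant change in the harmful direction. Sections 2.1 and 2.2b do define ICP and MAP changes in one direction, and the synopsis does so for all three pressures. This stands for ICP and MAP: a fall in ICP or a rise in MAP is not the harm the plan names, so the directional safety finding would not be wrong.

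Two further points also stand. Section 6.3 already promises means with 95% intervals, so a large opposite shift would be visible. And the figure of over 99.9% follows from any one-sided rule once the truth lies a full margin on the untested side. It shows what the label would say in that case and does not make the case likely; section 1.3 describes ICP increases with PEEP as small or absent and gives no basis for expecting a fall of 4 mm Hg.

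None of this makes the word correct. It is used for all three endpoints and again in the failure rule, so it is the prespecified verdict. The non-inferiority labels elsewhere show which claim 6.3 should state. For CPP the appeal to a one-directional definition fails, because 2.2a points the other way.

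**Conclusion.** The point holds as a fault in the stated conclusion. Section 6.3 draws equivalence from rules that test one side only. If the true mean shift in the untested direction were one full margin, the label would be applied in over 99.9% of trials, against about 5% under a two-sided equivalence rule. This rests on n = 18, the SDs and margins of 6.4 and the one-sided 95% bound of 6.4, and it holds whichever way the SDs are read.

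A reader might infer more, and the documents do not support it.
- **That the test is wrong or the safety conclusion invalid.** The rule is a sound non-inferiority rule and its error on the harmful side, as 6.3 tests it, is 5%.
- **That the trial is underpowered.** This would assume an equivalence aim that the design statements contradict. Even then, power at n = 18 and zero change would be 72%, 69% and 63% (ICP, CPP, MAP) with the formula of step 1, but about 97%, 97% and 95% if the SDs are of the change. The plan does not say which applies, so no loss of power is claimed.

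**What to change.** In section 6.3:
- Replace the equivalence verdicts with non-inferiority: ICP is non-inferior (mean increase less than 4 mm Hg) if the one-sided 95% upper bound of the change is below 4; MAP is non-inferior (mean decrease less than 10 mm Hg) if the one-sided 95% lower bound is above −10. Say that these are the one-sided bounds of 6.4.
- Replace the equivalence wording in the failure sentence for CPP and MAP with non-inferiority.
- Add that a mean change in the other direction is reported with its two-sided 95% interval and is not called equivalent.
- Before the CPP sentence is finalised, reconcile section 2.2a (increase) with the synopsis and 6.3 (decrease), so that objective, rule and adverse event definition name the same direction.

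Margins, bounds, sample size, data and procedures do not change. The cost is a few sentences of rewording, and the report can no longer claim equivalence.
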